#### **8.3.1.1. Reporting SAEs to Pfizer Safety**

All SAEs occurring in a participant during the active collection period are reported to Pfizer Safety on the CT SAE Report Form immediately and under no circumstance should this exceed 24 hours, as indicated in [Appendix 3](#). The investigator will submit any updated SAE data to the Sponsor within 24 hours of it being available.

SAEs occurring in a participant after the active collection period has ended are reported to Pfizer Safety if the investigator becomes aware of them; at a minimum, all SAEs that the investigator believes have at least a reasonable possibility of being related to IP must be reported to Pfizer Safety.

#### **8.3.1.2. Recording Nonserious AEs and SAEs on the CRF**

During the active collection period, both nonserious AEs and SAEs are recorded on the CRF.

#### **8.3.2. Method of Detecting AEs and SAEs**

The method of recording, evaluating, and assessing causality of AEs and SAEs and the procedures for completing and transmitting SAE reports are provided in [Appendix 3](#).

Care will be taken not to introduce bias when detecting AEs and/or SAEs. Open-ended and nonleading verbal questioning of the participant is the preferred method to inquire about AE occurrences.

#### **8.3.3. Follow-up of AEs and SAEs**

After the initial AE/SAE report, the investigator is required to proactively follow each participant at subsequent visits/contacts. For each event, the investigator must pursue and obtain adequate information until resolution, stabilization, the event is otherwise explained, or the participant is lost to follow-up (as defined in [Section 7.3](#)).

In general, follow-up information will include a description of the event in sufficient detail to allow for a complete medical assessment of the case and independent determination of possible causality. Any information relevant to the event, such as concomitant medications and illnesses, must be provided. In the case of a participant death, a summary of available autopsy findings must be submitted as soon as possible to Pfizer Safety.

Further information on follow-up procedures is given in [Appendix 3](#).

#### **8.3.4. Regulatory Reporting Requirements for SAEs**

Prompt notification by the investigator to the Sponsor of an SAE is essential so that legal obligations and ethical responsibilities towards the safety of participants and the safety of a study intervention under clinical investigation are met.

The Sponsor has a legal responsibility to notify both the local regulatory authority and other regulatory agencies about the safety of a study intervention under clinical investigation. The Sponsor will comply with country-specific regulatory requirements relating to safety reporting to the regulatory authority, institutional review boards (IRBs)/ethics committees (ECs), and investigators.

Investigator safety reports must be prepared for suspected unexpected serious adverse reactions (SUSARs) according to local regulatory requirements and Sponsor policy and forwarded to investigators as necessary.

An investigator who receives an investigator safety report describing an SAE or other specific safety information (eg, summary or listing of SAEs) from the Sponsor will review and then file it along with the investigator's brochure and will notify the IRB/EC, if appropriate according to local requirements.

#### **8.3.5. Exposure During Pregnancy or Breastfeeding, and Occupational Exposure**

Exposure to the IP under study during pregnancy or breastfeeding and occupational exposure are reportable to Pfizer Safety within 24 hours of investigator awareness.

##### **8.3.5.1. Exposure During Pregnancy**

Details of all pregnancies in female partners of male participants will be collected after the start of study intervention and until 3 weeks after the last dose.

If a pregnancy is reported, the investigator should inform the Sponsor within 24 hours of learning of the pregnancy and should follow the procedures outlined in [Appendix 4](#).

Abnormal pregnancy outcomes (eg, spontaneous abortion, fetal death, stillbirth, congenital anomalies, ectopic pregnancy) are considered SAEs.

##### **8.3.5.2. Exposure During Breastfeeding**

Scenarios of exposure during breastfeeding must be reported, irrespective of the presence of an associated SAE, to Pfizer Safety within 24 hours of the investigator's awareness, using the CT SAE Report Form. An exposure during breastfeeding report is not created when a Pfizer drug specifically approved for use in breastfeeding women (eg, vitamins) is administered in accord with authorized use. However, if the infant experiences an SAE associated with such a drug's administration, the SAE is reported together with the exposure during breastfeeding.

### 8.3.5.3. Occupational Exposure

An occupational exposure occurs when, during the performance of job duties, a person (whether a healthcare professional or otherwise) gets in unplanned direct contact with the product, which may or may not lead to the occurrence of an AE.

An occupational exposure is reported to Pfizer Safety within 24 hours of the investigator's awareness, using the CT SAE Report Form, regardless of whether there is an associated SAE. Since the information does not pertain to a participant enrolled in the study, the information is not recorded on a CRF; however, a copy of the completed CT SAE Report Form is maintained in the investigator site file.

### 8.3.6. Medication Errors

Medication errors may result from the administration or consumption of the IP by the wrong participant, or at the wrong time, or at the wrong dosage strength.

Exposures to the IP under study may occur in clinical trial settings, such as medication errors.

Safety Event	Recorded on the CRF	Reported on the CT SAE Report Form to Pfizer Safety Within 24 Hours of Awareness
Medication errors	All (regardless of whether associated with an AE)	Only if associated with an SAE

Medication errors include:

- Medication errors involving participant exposure to the IP;
- Potential medication errors or uses outside of what is foreseen in the protocol that do or do not involve the study participant.

Such medication errors occurring to a study participant are to be captured on the medication error page of the CRF, which is a specific version of the AE page.

In the event of a medication dosing error, the Sponsor should be notified immediately.

Whether or not the medication error is accompanied by an AE, as determined by the investigator, the medication error is recorded on the medication error page of the CRF and, if applicable, any associated AE(s), serious and nonserious, are recorded on an AE page of the CRF.

Medication errors should be reported to Pfizer Safety within 24 hours on a CT SAE Report Form only when associated with an SAE.

#### **8.4. Treatment of Overdose**

For this study, any dose of dacomitinib greater than 30 mg will be considered an overdose.

The Sponsor does not recommend specific treatment for an overdose.

In the event of an overdose, the investigator/treating physician should:

1. Contact the medical monitor immediately.
2. Closely monitor the participant for any AEs/SAEs and laboratory abnormalities until dacomitinib can no longer be detected systemically (at least 17 days,  $5 \times$  dacomitinib half-life).
3. Obtain a blood sample for PK analysis within 1 day from the date of the last dose of study intervention if requested by the medical monitor (determined on a case-by-case basis).
4. Document the quantity of the excess dose as well as the duration of the overdose in the CRF.
5. Overdose is reportable to Safety only when associated with an SAE.

Decisions regarding dose interruptions or modifications will be made by the investigator in consultation with the medical monitor based on the clinical evaluation of the participant.

#### **8.5. Pharmacokinetics**

##### **8.5.1. Pharmacokinetic Assessment of Dacomitinib and PF-05199265**

Blood samples of approximately 3 mL, to provide a minimum of 1 mL of plasma, will be collected into appropriately labeled tubes containing dipotassium ethylenediamine tetraacetic acid ( $K_2EDTA$ ) at each specified time point for measurement of plasma concentrations of dacomitinib and its metabolite PF-05199265 as specified in the [SoA](#). Instructions for the collection and handling of biological samples will be provided in the laboratory manual or by the Sponsor. The actual date and time (24-hour clock time) of each sample will be recorded.

The actual times may change, but the number of samples will remain the same. All efforts will be made to obtain the samples at the exact nominal time relative to dosing. Collection of samples up to and including 10 hours after dose administration that are obtained within 10% of the nominal time (eg, within 6 minutes of a 60-minute sample) relative to dosing will not be captured as a protocol deviation, as long as the exact time of the collection is noted on the source document and data collection tool (eg, CRF). Collection of samples more than 10 hours after dose administration that are obtained  $\leq 1$  hour away from the nominal time relative to dosing will not be captured as a protocol deviation, as long as the exact time of the collection is noted on the source document and data collection tool (eg, CRF).

Samples will be used to evaluate the PK of dacomitinib and PF-05199265. Samples collected for analyses of dacomitinib and PF-05199265 plasma concentration may also be used to evaluate safety or efficacy aspects related to concerns arising during or after the study, for metabolite identification and/or evaluation of the bioanalytical method, or for other internal exploratory purposes.

Genetic analyses will not be performed on these plasma samples unless consent for this was included in the informed consent. Participant confidentiality will be maintained.

Samples collected for measurement of plasma concentrations of dacomitinib and PF-05199265 will be analyzed using a validated analytical method in compliance with applicable standard operating procedures (SOPs).

The PK samples must be processed and shipped as indicated in the instructions provided to the investigator site to maintain sample integrity. Any deviations from the PK sample handling procedure (eg, sample collection and processing steps, interim storage or shipping conditions), including any actions taken, must be documented and reported to the Sponsor. On a case-by-case basis, the Sponsor may make a determination as to whether sample integrity has been compromised.

#### **8.5.2. Protein Binding Assessment**

Blood samples (10 mL of blood to obtain 4 ml of plasma) for protein binding analysis will be collected into appropriately labeled tubes containing K2EDTA at times specified in the [SoA](#). The actual times may change but the number of samples will remain the same. All efforts will be made to obtain the protein binding samples at the exact nominal time relative to dosing. However, samples obtained within 10% of the nominal time (eg, within 6 minutes of a 60 minute sample) from dosing will not be captured as a protocol deviation, as long as the exact time of the sample collection is noted on the source document and data collection tool (eg, CRF).

Samples will be analyzed using a validated analytical method in compliance with Pfizer SOPs.

The blood samples must be processed and shipped as indicated in the instructions provided to the investigator site to maintain sample integrity. Any deviations from the sample handling procedure (eg, sample collection and processing steps, interim storage or shipping conditions), including any actions taken, must be documented and reported to the Sponsor. On a case-by-case basis, the Sponsor may make a determination as to whether sample integrity has been compromised.

#### **8.6. Pharmacodynamics**

Pharmacodynamic (PD) parameters are not evaluated in this study.

## **8.7. Genetics**

### **8.7.1. CYP2D6 Genotyping Analysis**

A 3-mL blood sample for deoxyribonucleic acid (DNA) isolation will be collected. DNA samples will be analyzed for the purpose of determining the genotype of CYP2D6.

Genes for other drug-metabolizing enzymes or transporters suspected to be involved in the metabolism and/or excretion of dacomitinib may also be evaluated. No other genes will be analyzed.

In the event of DNA extraction failure, a replacement genetic blood sample may be requested from the participant.

See [Appendix 5](#) for information regarding genetic research. Details on processes for collection and shipment of these samples can be found in the laboratory manual or by the Sponsor.

### **8.7.2. Banked Biospecimens for Genetics**

A 4-mL blood sample optimized for DNA isolation Prep D1 will be collected as local regulations and IRBs/ECs allow.

Banked biospecimens may be used for research related to drug response. Genes and other analytes (eg, proteins, ribonucleic acid (RNA), nondrug metabolites) may be studied using the banked samples.

Unless prohibited by local regulations or IRB/EC decision, participants will be asked to indicate on the consent document whether they will allow their banked biospecimens to also be used to design and conduct research in order to gain a further understanding of other diseases and to advance science, including development of other medicines for patients. This component of the sampling banking is optional for participants; they may still participate in the study even if they do not agree to the additional research on their banked biospecimens. The optional additional research does not require the collection of any further samples.

See [Appendix 5](#) for information regarding genetic research. Details on processes for collection and shipment of these samples can be found in laboratory manual or by the Sponsor.

## **8.8. Biomarkers**

Biomarkers are not evaluated in this study.

## **8.9. Health Economics**

Health economics/medical resource utilization and health economics parameters are not evaluated in this study.

## 9. STATISTICAL CONSIDERATIONS

Detailed methodology for summary and statistical analyses of the data collected in this study is outlined here and further detailed in a statistical analysis plan (SAP), which will be maintained by the Sponsor. The SAP may modify what is outlined in the protocol where appropriate; however, any major modifications of the primary endpoint definitions or their analyses will also be reflected in a protocol amendment.

### 9.1. Statistical Hypotheses

Not applicable.

### 9.2. Sample Size Determination

Approximately 18 participants will be enrolled into the study to ensure 6 PK evaluable participants in each of the 2 cohorts. This sample size is consistent with recommendations from the Food and Drug Administration (FDA) Guidance for Industry: Pharmacokinetics in Patients with Impaired Hepatic Function: Study Design, Data Analysis, and Impact on Dosing and Labeling (issued by Center for Drug Evaluation and Research [CDER]/ Center for Biologics Evaluation and Research [CBER], May 2003).

### 9.3. Populations for Analysis

Population	Description
Safety	All participants assigned to dacomitinib and who take 1 dose of dacomitinib.
PK Concentration	All participants who take 1 dose of dacomitinib and have at least 1 dacomitinib plasma concentration.
PK parameter	All participants who take 1 dose of dacomitinib and have at least 1 dacomitinib plasma PK parameters of primary interest.

### 9.4. Statistical Analyses

The SAP will be developed and finalized before database lock and will describe the participant populations to be included in the analyses, and procedures for accounting for missing, unused, and spurious data. This section is a summary of the planned statistical analyses of the primary and secondary endpoints.

#### 9.4.1. Efficacy Analyses

An efficacy analysis is not applicable to this study.

#### 9.4.2. Safety Analyses

AEs, ECGs, BP, pulse rate, and safety laboratory test data will be reviewed and summarized on an ongoing basis during the study to evaluate the safety of participants. Any clinical laboratory test, ECG, BP, and pulse rate abnormalities of potential clinical concern will be described. Safety data will be presented in tabular and/or graphical format and summarized descriptively by cohort, where appropriate.

Medical history and physical examination information, as applicable, collected during the course of the study will be considered source data and will be required to be reported, unless otherwise noted. However, any untoward findings identified on physical examinations conducted during the active collection period will be captured as AEs, if those findings meet the definition of an AE. Data collected at Screening that are used for inclusion/exclusion criteria, such as laboratory data, ECGs, and vital signs, will be considered source data, and will be required to be reported, unless otherwise noted. Demographic data collected at Screening will be reported.

#### 9.4.2.1. Electrocardiogram Analyses

Changes from baseline for the ECG parameters QT interval, heart rate, QTc interval, PR interval, and QRS complex will be summarized by cohort and time.

The number (%) of participants with maximum post-dose QTc values and maximum increases from baseline in the following categories will be tabulated by cohort:

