### **5.2.2. Additional Exclusion Criteria for Participants with Normal Hepatic Function (Cohort 2)**

In addition, participants in the normal hepatic function cohort (Cohort 2) presenting with any of the following will not be included in the study:

1. Evidence or history of clinically significant hematological, renal, endocrine, pulmonary, gastrointestinal, cardiovascular, hepatic, psychiatric, neurologic, or allergic disease (including drug allergies deemed relevant for participation in this study, but excluding untreated, asymptomatic, seasonal allergies at the time of dosing).
2. History of regular alcohol consumption exceeding 7 drinks/week for females or 14 drinks/week for males (1 drink = 5 ounces (150 mL) of wine or 12 ounces (360 mL) of beer or 1.5 ounces (45 mL) of hard liquor) within 6 months of Screening.
3. Screening supine BP  $\geq 140$  mm Hg (systolic) or  $\geq 90$  mm Hg (diastolic), following at least 5 minutes of supine rest. If initial supine BP is  $\geq 140$  mm Hg (systolic) or  $\geq 90$  mm Hg (diastolic), the BP should be repeated 2 more times and the average of the 3 BP values should be used to determine the participant's eligibility.
4. Screening 12-lead ECG demonstrating corrected QT (Fridericia method) (QTcF)  $> 450$  msec and/or a QRS complex  $> 120$  msec. If initial QTcF exceeds 450 msec, or QRS complex exceeds 120 msec, the ECG should be repeated 2 more times and the average of the three QTcF and/or QRS complex values should be used to determine the participant's eligibility.
5. Use of prescription or nonprescription drugs and dietary supplements within 7 days or 5 half-lives (whichever is longer) prior to the first dose of study medication. As an exception, acetaminophen/paracetamol may be used at doses of  $\leq 1$  g/day. Limited use of nonprescription medications that are not believed to affect participant safety or the overall results of the study may be permitted on a case by case basis following approval by the Sponsor. Herbal supplements and hormone replacement therapy must have been discontinued at least 28 days prior to the dose of dacomitinib.
6. Participants with a history of or current positive results for hepatitis B or hepatitis C, including hepatitis B surface antigen (HepBsAg), hepatitis B core antibody (HepBcAb), or hepatitis C antibody (HCVAb).

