### **5.2.3. Additional Exclusion Criteria for Participants with Severely Impaired Hepatic Function (Cohort 1)**

1. Other clinically significant disease that contraindicates study drug or that may affect the PK of dacomitinib (stable, chronic, controlled disorders such as hypertension and diabetes may be acceptable upon Sponsor agreement).
2. Hepatic carcinoma and hepatorenal syndrome.

3. Undergone porta-caval shunt surgery.

NOTE: Participants with a transjugular intrahepatic portosystemic shunt (TIPS) are permitted provided that they meet the Child-Pugh classification criteria.

4. History of gastrointestinal hemorrhage due to esophageal varices or peptic ulcers less than 1 month prior to study entry.
5. Any clinically significant laboratory abnormality except for those parameters influenced by hepatic impairment.
6. Participants with an estimated glomerular filtration rate (eGFR) of  $\leq 60$  mL/min/1.73 m^2 based on the Modification of Diet in Renal Disease (MDRD) equation, with a single repeat permitted to assess eligibility, if needed;
7. Presence of clinically active Stage 3 or 4 encephalopathy.
8. Severe uncontrolled ascites and/or pleural effusion.
9. Screening supine blood pressure  $\geq 160$  mm Hg (systolic) or  $\geq 90$  mm Hg (diastolic), on a single measurement following at least 5 minutes of rest. If initial supine BP is  $\geq 160$  mm Hg (systolic) or  $\geq 90$  mm Hg (diastolic), the BP should be repeated two more times and the average of the three BP values should be used to determine the participant's eligibility.
10. Screening supine 12-lead ECG demonstrating QTcF  $> 470$  msec. If initial QTcF exceeds 470 msec, the ECG should be repeated two more times and the average of the three QTcF values should be used to determine the participant's eligibility.

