### **8.2.3. Electrocardiograms**

Single or triplicate 12-Lead ECG should be collected at times specified in the [SoA](#) section of this protocol using an ECG machine that automatically calculates the heart rate and measures PR, QT, and corrected QT (QTc) intervals and QRS complex. All scheduled ECGs should be performed after the participant has rested quietly for at least 10 minutes in a supine position.

Triplicate 12-lead ECGs will be obtained approximately 2 to 4 minutes apart; the average of the triplicate ECG measurements collected on Day 1 at predose will serve as each participant's time-controlled baseline QTc value.

To ensure safety of the participants, a qualified individual at the investigator site will make comparisons to baseline measurements. Additional ECG monitoring will occur if a) a postdose QTc interval is increased by  $\geq 30$  msec from the baseline **and** is  $> 450$  msec; or b) an absolute QTc value is  $\geq 500$  msec for any scheduled ECG. If either of these conditions occurs, then 2 additional ECGs will be collected approximately 2 to 4 minutes apart to confirm the original measurement. If the QTc values from these repeated ECGs remain above the threshold value, then a single ECG must be repeated at least hourly until QTc values from 2 successive ECGs fall below the threshold value that triggered the repeat measurement.

If a postdose QTc interval remains  $\geq 30$  msec from the baseline **and** is  $> 450$  msec; or b) an absolute QTc value is  $\geq 500$  msec for any scheduled ECG for greater than 4 hours (or sooner, at the discretion of the investigator), or QTc intervals get progressively longer, the participant should undergo continuous ECG monitoring. A cardiologist should be consulted if QTc intervals do not return to less than the criterion listed above after 8 hours of monitoring (or sooner, at the discretion of the investigator).

In some cases, it may be appropriate to repeat abnormal ECGs to rule out improper lead placement as contributing to the ECG abnormality. It is important that leads be placed in the same positions each time in order to achieve precise ECG recordings. If a machine-read QTc value is prolonged, as defined above, repeat measurements may not be necessary if a qualified medical provider's interpretation determines that the QTc values are in the acceptable range.

ECG values of potential clinical concern are listed in [Appendix 7](#).

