##### Safety QTc Assessment

Degree of Prolongation	Mild (msec)	Moderate (msec)	Severe (msec)
Absolute value	>450-480	>480-500	>500
Increase from baseline		30-60	>60

In addition, the number of participants with uncorrected QT values >500 msec will be summarized.

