HepBcAb	hepatitis B core antibody
HepBsAg	hepatitis B surface antigen
HCVAb	hepatitis C antibody
HIPAA	Health Insurance Portability and Accountability Act
HIV	human immunodeficiency virus
HRT	hormone replacement therapy
IB	investigator's brochure
ICD	informed consent document
ICH	International Council for Harmonisation
ID	identification
IGF1R	insulin-like growth factor 1 receptor
IM	intermediate metabolizer
IND	investigational new drug
INR	international normalized ratio
IP	investigational product
IRB	institutional review board
IRC	internal review committee
IRT	interactive response technology
IUD	intrauterine device
IUS	intrauterine hormone-releasing system
IV	intravenous
JAK3	janus kinase 3
K 2 EDTA	dipotassium ethylenediamine tetraacetic acid
LFT	liver function test
MDRD	Modification of Diet in Renal Disease
MET	mesenchymal-epithelial transition
MRI	magnetic resonance imaging
N/A	not applicable
NCI	National Cancer Institute

Abbreviation	Term
NSCLC	non-small cell lung cancer
OAT	organic anion transporter
OATP	organic anion transporting polypeptide
OCT	organic cation transporter
PCD	primary completion date
PD	pharmacodynamic(s)
PDGFR	platelet-derived growth factor receptor
PGx	pharmacogenomic(s)
P-gp	P-glycoprotein
PI	principal investigator
PI3K	phosphoinositide 3-kinase
PK	pharmacokinetic(s)
PPI	proton-pump inhibitor
PR	pulse rate
PT	prothrombin time
QD	once daily
QTc	corrected QT
QTcB	corrected QT (Bazett method)
QTcF	corrected QT (Fridericia method)
qual	qualitative
RBC	red blood cell
RNA	ribonucleic acid
ROS1	ROS oncogene 1
RTK	receptor tyrosine kinase
rCYP	recombinant cytochrome P450
SAE	serious adverse event
SAP	statistical analysis plan
SCr	serum creatinine
SoA	schedule of activities
SOP	standard operating procedure
SRSD	single reference safety document
SToD	study team on demand
SUSAR	suspected unexpected serious adverse reaction
$t_{1/2}$	terminal phase half-life
Tbili	total bilirubin
TIPS	transjugular intrahepatic portosystemic shunt
$T_{max}$	time to reach the maximum observed plasma concentration
UGT	uridine diphosphate glucuronosyltransferase
ULN	upper limit of normal
US	United States
$V_z/F$	apparent volume of distribution
$V_{z,u}/F$	Unbound $V_z/F$
WBC	white blood cell
WOCBP	woman of childbearing potential

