### **8.2.7. ECG Data**

The baseline measurement is the predose measurement.

*Changes from baseline for the ECG parameters QT interval, heart rate, QTc interval, PR interval, and QRS complex will be summarized by cohort and time.*

*The number (%) of participants with maximum post-dose QTc values and maximum increases from baseline in the following categories will be tabulated by cohort:*

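### Does the absolute Mild QTc cell mislead between cohorts because the two cohorts have different QTcF entry limits?

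*Protocol*

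**What the plan says.** Protocol 9.4.2.1 sets the display: "The number (%) of participants with maximum post-dose QTc values and maximum increases from baseline in the following categories will be tabulated by cohort". The table that follows, headed "Degree of Prolongation", has two rows. The absolute row runs >450-480 (Mild), >480-500 (Moderate) and >500 msec (Severe). The increase row has no Mild entry and runs 30-60 (Moderate) and >60 msec (Severe). SAP 8.2.7 repeats the table.

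The entry rules differ by cohort. For Cohort 2, Protocol 5.2.2 says "If initial QTcF exceeds 450 msec, or QRS complex exceeds 120 msec, the ECG should be repeated 2 more times". Eligibility then rests on the mean of all three readings. For Cohort 1, Protocol 5.2.3 says "If initial QTcF exceeds 470 msec, the ECG should be repeated two more times", with the same averaging rule.

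Baseline is settled. Protocol 8.2.3 states that "the average of the triplicate ECG measurements collected on Day 1 at predose will serve as each" participant's baseline QTc, and SAP 8.2.7 says "The baseline measurement is the predose measurement". Both documents also summarize ECG changes from baseline by cohort and time. The SAP lists the ECG data, and Protocol 9.4.2 adds: "Any clinical laboratory test, ECG, BP, and pulse rate abnormalities of potential clinical concern will be described".

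**The concern.** A cell labelled as a degree of prolongation suggests that something lengthened after dosing. The Mild absolute cell does not require that: it counts any maximum post-dose value in its range, whatever the participant started with. Because Cohort 1 may enter with a QTcF between 450 and 470 msec and Cohort 2 in general may not, the cell can fill faster in Cohort 1 with no drug effect at all.

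ECG findings belong to the secondary safety endpoint (Protocol section 3). With 8 participants per cohort, one count is 1/8 = 12.5 percentage points. A reader who compares only this cell between cohorts could take a difference in starting QTc for an effect of dosing in severe hepatic impairment. The table also says only QTc, while the abbreviation list defines both the Bazett and the Fridericia correction.

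**Working it through.** The plan gives no QTc mean, SD or target count, so there is no stated figure to reproduce. The check is interval arithmetic, then an illustration under stated assumptions.

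**1. Overlap.** Limits are from Protocol 5.2.2 and 5.2.3; cells are from 9.4.2.1.
- Band between the two limits: 470 − 450 = 20 msec.
- Width of the Mild cell: 480 − 450 = 30 msec.
- Share of the cell covered: 20/30 = 67%.
- The next cell starts at 480 msec, above both limits, so only the Mild cell is affected.

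**2. Two example participants.**
- 460 falling to 455 msec: counted as Mild; change −5; not in the increase row.
- 445 rising to 455 msec: counted as Mild; change +10; not in the increase row.

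The table alone does not separate them. The listing does, and their changes of −5 and +10 enter the change-from-baseline summary with the correct sign.

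**3. Effect of the entry limits alone.** Assumptions: QTcF; true values normal with the same mean in both cohorts; between-person SD 15 or 20 msec; within-person SD 8 or 10 msec; no drug effect. Screening is one reading and, if that is above the limit, the mean of three must be at or below it. Baseline is the mean of three readings. Post-dose is the larger of two single readings (6 hours and Day 7, as in the Schedule of Activities). Gap in participants = 8 × gap in percentage points / 100.

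| Assumed mean (msec) | Gap in Mild cell, Cohort 1 − Cohort 2 (points) | Gap in participants, of 8 | Cohort 2 candidates failing the QTcF screen |
|---|---|---|---|
| 410 | 0.28 to 1.55 | 0.02 to 0.12 | 0.4 to 2.1% |
| 420 | 1.49 to 4.18 | 0.12 to 0.33 | 2.1 to 5.9% |
| 430 | 4.91 to 8.95 | 0.39 to 0.72 | 8.0 to 13.9% |
| 440 | 10.79 to 15.27 | 0.86 to 1.22 | 21.5 to 27.3% |

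The last row is the edge of the range, since it implies that more than a fifth of healthy candidates fail on QTcF.

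**4. Where the gap sits.** At mean 430 and SDs 20 and 8, Cohort 1's 21.0% in the cell splits into 8.5% with baseline at or below 450 and 12.4% above it (rounded). Cohort 2's 12.0% splits into 8.0% and 4.1%. Of the 8.95-point gap, 8.42 points come from baselines above 450: 8.42/8.95 = 94%. Cohort 2 is not empty above 450, because its limit applies at screening and a first reading above 450 can still pass on the average of three.

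**5. The neighbouring row.** Under the same model the share with an increase of at least 30 msec is about 0.1% (SDs 15 and 8) or 0.9% (SDs 20 and 10), about equal in the two cohorts at every mean. The entry limits do not distort it.

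**6. Would another summary do better?** If Cohort 1 really has a higher mean, say 430 against 410, the Mild cell holds 16.8 to 22.8% against 1.2 to 4.0%. Matched by SD pair, the gap is 15.6 to 18.8 points, or 1.25 to 1.50 of 8 participants. A count of participants whose category worsened still shows 8.9 to 11.8% against 1.0 to 3.1% with no drug effect. A full baseline-by-post-dose cross-tabulation has 4 × 4 = 16 cells per cohort for 8 to 10 people.

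**The case for a change.** The best case for a change is that the increase row starts at 30 msec, so it cannot tell a small new crossing of 450 from a participant who was already above it. The change summaries are for the group, not the person. Only the listing separates the two examples in step 2. A cross-tabulation would show the split at a glance from data already collected, at almost no cost, and the cell concerns a secondary safety endpoint.

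Most of the facts in this stand: the cell does mix starting value with post-dose change, and the higher Cohort 1 limit makes that mixing more likely there. What does not stand is that a reader is left without the means to interpret it. The row is labelled as an absolute value, and the row beneath it gives the increase. The change summary shows whether QTc moved in either cohort. Reading a listing of 8 to 10 people is no burden, and it shows more than a sparse 16-cell table. The 12.5-point figure is the weight of any single count among 8, not the size of this effect; with the permitted maximum of 10 in Cohort 2 it would be 10 points there.

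The unnamed QT correction is a small gap that analysts will fill sensibly. Eligibility and Appendix 7 both use Fridericia, and Bazett appears only in the abbreviation list.

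**Conclusion.** No change is needed. The Mild absolute cell can be fuller in Cohort 1 for reasons unrelated to dosing, but the plan already reports what is needed to see this. The safety conclusion from the plan as written stays sound. Protocol 9.1 and SAP 4.1 and 4.2 set no hypothesis or decision rule, and the primary PK comparison is untouched.

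The size is modest: with equal means, well under one participant in 8 at assumed means of 410 to 430 msec and about one at 440. These figures rest wholly on assumed means and SDs, on QTcF being the correction tabulated, and on no drug effect. A true difference in baseline means would widen the gap, but a worsened-category count would not remove it. If an analyst chooses to footnote how many participants in the cell had a baseline above 450 msec, that is a matter of table layout. Protocol section 9 lets the SAP modify its outline and asks for an amendment only for major changes to the primary endpoints or their analyses.
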